7.5 Appendix E. Psychological measures

Measures	Questions

Example telehealth screener interview questions
	
Age Verification: “To confirm, can I ask your age?”
 
Fluency and understanding of English: “Are you fluent in English and able to understand the study information if it were presented to you in written format?”
 
Previous Trauma “Without going into detail, what type of trauma have you experienced? (e.g., war, childhood, disaster)
 
Symptoms “What symptoms do you experience?”
 
Previous diagnosis of PTSD: “Have you been diagnosed with Post-Traumatic Stress Disorder (PTSD) by a healthcare professional previously?”
 
Current Treatment Team: If yes, “do you have a current treating mental health team managing your PTSD or any other mental health conditions?”
 
Other Psychiatric Diagnoses: “Have you ever been diagnosed with any of the following conditions?” Complex PTSD Psychosis Bipolar Disorder Personality Disorder Substance Use Disorder
 
“What about other mental health diagnoses? Current or previously?” “Have you ever been hospitalised for your mental health?”
 
Medical History Related to Propranolol Use: “Do you have any of the following medical conditions that might make propranolol unsuitable for you? This could include asthma, heart disease, very low blood pressure, or diabetes.”
 
Allergies or Past Reactions: “Have you ever had any adverse reactions to propranolol or similar medications in the past?”
 
Current Medications: “Are you currently taking any medications that might interact with propranolol, such as other beta-blockers?”
 
Ability to Undergo Study Procedures: “Would you be comfortable undergoing an MRI scan and participating in psychological and biological assessments as part of the study?”
 
Willingness to Participate: “If eligible, would you be interested and willing to participate in this study and comply with the study procedures?”
 
“Are you able to attend the Thompson Institute, 1 day per week for 6 weeks, with blocks of assessments on either side of this?”

Example pre-assessment pack questionnaires
	
Peritraumatic distress inventory (PDI) 0 = Not at All True; 1 = Slightly True; 2 = Somewhat True; 3 = Very True; and 4 = Extremely True.
 
 1. I felt helpless 2. I felt sadness and grief 3. I felt frustrated or angry

Peritraumatic dissociative experiences questionnaire (PDEQ):

0 = Not at All True; 1 = Slightly True; 2 = Somewhat True; 3 = Very True; and 4 = Extremely True.

1. I had moments of losing track of what was going on – I “blanked out” or “spaced out” or in some way felt that I was not part of what was going on.
2. I found that I was on « automatic pilot » - I ended up doing things that I later realized I hadn't actively decided to do.
3. My sense of time changed – things seemed to be happening in slow motion.

PTSD Checklist for DSM-5 (PCL-5):

In the past week, how much were you bothered by:

(Not at all, A little bit, Moderately, Quite a bit, Extremely)

1. Repeated, disturbing, and unwanted memories of the stressful experience?
2. Repeated, disturbing dreams of the stressful experience?
3. Suddenly feeling or acting as if the stressful experience were actually happening again (as if you were actually back there reliving it)?

Beck Depression Inventory (BDI-I):

Copyrighted. Currently asking permissions to use.

Post-traumatic growth inventory (PTGI):

Indicate your score on a 6-point scale:

- 0 – I did not experience this as a result of my crisis.
 - 1 – I experienced this change to a very small degree as a result of my crisis.
 - 2 – I experienced this change to a small degree as a result of my crisis.
 - 3 – I experienced this change to a moderate degree as a result of my crisis.
 - 4 – I experienced this change to a great degree as a result of my crisis.
 - 5 – I experienced this change to a very great degree as a result of my crisis
1. I changed my priorities about what is important in life.
 2. I have a greater appreciation for the value of my own life.
 3. I have developed new interests.

WHO Quality of life (WHOQOL):

0 = Not at all; 1 = Not much; 2 = Moderately; 3 = A great deal; and 4 = Completely.

1. Do you get the kind of support from others that you need?
2. How would you rate your quality of life?
3. How satisfied are you with your health?

The Impact of Event Scale – Revised (IES-R)

0 = Not at all; 1 = A little bit; 2 = Moderately; 3 = Quite a bit; and 4 = Extremely

1. Any reminder brought back feelings about it
2. I had trouble staying asleep
3. Other things kept making me think about it

Childhood Trauma Questionnaire (CTQ)

Copyrighted. Currently asking permissions to use.

International Trauma Questionnaires (ITQ)

0 = Not at all; 1 = A little bit; 2 = Moderately; 3 = Quite a bit; and 4 = Extremely

1. Having upsetting dreams that replay part of the experience or are clearly related to the experience?
2. Having powerful images or memories that sometimes come into your mind in which you feel the experience is happening again in the here and now?
3. Avoiding internal reminders of the experience (for example, thoughts, feelings, or physical sensations)?

Pittsburgh Sleep Quality Index (PSQI)

0= Not during the past month; 1=Less than one week; 2=once or twice per week; 3=Three or more times per week

	
 1. Cannot get to sleep in 30 minutes 2. Wake up in the middle of the night or early morning 3. Have to get up to use the bathroom
Example semi-structured and structured interview questions	
Structured interview:
 
 1. Mini international neuropsychiatric interview (MINI) 
Semi-structured clinical interview: Under development.

7.6 Appendix F. CANTAB assessment

Participants will complete the CANTAB computerised cognitive assessment battery in person at the Thompson Institute. This will be done in the presence of the researcher and will take approximately 30mins. The assessments will cover cognitive domains such as memory, information processing and speed as well as executive functioning. The CANTAB is a fully automated, self-administered neuropsychological test battery presented on an iPad. Once the participant details have been entered, the majority of instructions are delivered by CANTAB and the participant responds as instructed by the CANTAB. The researcher is required to verbally explain two subtests (Motor Screening Task and Rapid Visual Information Processing task) to participants. Other researcher involvement is rarely required, usually only to pause a test protocol should a participant require a rest break. Tests will include:

1. Motor screening task (MOT)
2. Paired associates learning (PAL)
4. Reaction time task (RTI)
5. Spatial working memory (SWM)
6. Rapid visual information processing (RVP)

[figure not shown]
Motor Screening Task (MOT - CANTAB) – Verbal explanation provided by research staff

In addition to being a user-friendly way of introducing CANTAB tests to the participant, the Motor Screening Task provides a general assessment of whether sensorimotor deficits or lack of comprehension, will limit the collection of valid data from the participant. Administration time is 2minutes. Task format includes coloured crosses presented in different locations on the screen, one at a time. The participant must select the cross on the screen as quickly and accurately as possible. Outcome measures assess the participant's speed of response and the accuracy of pointing (selecting the cross).

Paired Associates Learning (PAL - CANTAB)

Paired Associates Learning assesses visual memory and new learning. Administration time is 8minutes. Task format includes boxes displayed on the screen and are “opened” in a randomised order. One or more of them will contain a pattern. The patterns are then displayed in the middle of the screen, one at a time and the participant must select the box in which the pattern was originally located. If the participant makes an error, the boxes are opened in sequence again to remind the participant of the locations of the patterns. Increased difficulty levels can be used to test high-functioning, healthy individuals. Outcome measures include the errors made by the participant, the number of trials required to locate the pattern(s) correctly, memory scores and stages completed.

[figure not shown]
Reaction Time (RTI - CANTAB)

Reaction Time provides assessments of motor and mental response speeds, as well as measures of movement time, reaction time, response accuracy and impulsivity. Administration time is 3 minutes. Task format includes the participant selecting and holding a button at the bottom of the screen. Circles are presented above (one for the simple mode, and five for the five-choice mode.) In each case, a yellow dot will appear in one of the circles, and the participant must react as soon as possible, releasing the button at the bottom of the screen, and selecting the circle in which the dot appeared. Outcome measures are divided into reaction time and movement time for both the simple and five-choice variants.

Spatial Working Memory (SWM - CANTAB)

Spatial Working Memory requires retention and manipulation of visuospatial information. This self-ordered test has notable executive function demands and provides a measure of strategy as well as working memory errors. Administration time is 4 minutes. Task format includes beginning with a number of coloured squares (boxes) shown on the screen. The aim of this test is that by selecting the boxes and using a process of elimination, the participant should find one yellow 'token' in each of a number of boxes and use them to fill up an empty column on the right-hand side of the screen. Depending on the difficulty level used for this test, the number of boxes can be gradually increased until a maximum of 12 boxes are shown for the participants to search. The colour and position of the boxes used are changed from trial to trial to discourage the use of stereotyped search strategies. Outcome measures include errors (selecting boxes that have already been found to be empty and revisiting boxes which have already been found to contain a token) and strategy.

Rapid Visual Processing (RVP - CANTAB) - Verbal explanation provided by research staff

Rapid Visual Information Processing is a measure of sustained attention. Administration time is 7 minutes. Task format includes a white box shown in the centre of the screen, inside which digits from 2 to 9 appear in a pseudo-random order, at the rate of 100 digits per minute. Participants are requested to detect target sequences of digits (for example, 2-4-6, 3-5-7, 4-6-8). When the participant sees the target sequence, they must respond by selecting the button in the centre of the screen as quickly as possible. The level of difficulty varies with either one- or three-target sequences that the participant must watch for at the same time. Outcome measures cover latency (speed of response), probability of false alarms and sensitivity

7.7. Appendix G. Propranolol indications, side effects and warnings

List of Beta-blockers	
Acebutolol	Sectral
Atenolol	Beta Adalat, Betatop, Tenordate, Tenoretic, Tenormin, Betanol.
Betaxolol	Betoptic, Kerlone
Bisoprolol	Monacor, Zebeta.
Carteolol	Carpilo, Carteol, Mikelan, Ocupress
Carvedilol	Coreg, Kredex
Celiprolol	Cardem, Selectol, Celipres, Celipro, Celol, Cordiax, Dilanorm
Esmolol	Brevibloc
Labetalol	Trandate, Normodyne
Levobunolol	Betagan, Ratio-Levobunolol
Metipranolol	Optipranolol
Metoprolol	Lopressor, Metoprolol Tartrate, Toprol.
Nadolol	Corgard
Nebivolol	Bystolic
Pindolol	Visken
Propranolol	Inderal, InnoPran XL, Hemangeol, Deralin.
Sotalol	Betapace, Sotylize.
Tertatolol	Artex, Artexal, Prenalex,
Timolol	Blocadren, Timolol Maleate-EX, Betimol, Istalol, Timoptic, Combigan, Digaol, Duotrav, Gaoptol, Nyogel, Nyolol, Moducen, Nyogel, Nyolol, Ophtim, Pilobloq, Timabak, Timocomod, Timoptol, Xalacom, Azarga, Cosopt, Dorzaolamide, Ganfort, Geltim, Timacor
List of drugs that may interact with propranolol	
Contraindicated	
Floctafenine	Floctafenine AA Pharma, Idarac
Sulpiride	Dogmatil, Bosnyl, Dogmil, Dolmatil, Eglonyl, Sulpitil, Sulpor, Sulparex, Meresa
Not Recommended	
Diltiazem	Cardizem, Cartia XT, Tiazac, Dilt-XR, Dilacorxr, Felodipine, Plendil
Verapamil	Calan, Isoptin, Verelan, Covera, Verapamil, Verap.
Fingolimod	Gilenya, Novartis
Precautions Required	
Amiodarone	Pacerone, Cordarone, Nexterone
Halogenated Volatile Anesthetics	
Antihypertensives (Central alpha agonists):	
Clonidine	Catapres, Jenloga, Kapvay
Guanfacine	Intuniv, Tenex.
Moxonidine	Physiotens
Rilmenidine	Albarel, Hyperium, Iterium, Tenaxum
Balcofen	Lioresal, Gablofen, Kemstro.
Ergotamine	Migergot, Ergomar, Cafergot
Fluvoxamine	Luvox
Insulin	
Hypoglycemic Sulfonamides	

Gilbornuride	Glutril
Gliclazide	Gliclazide, Diamicon
Glimepiride	Amaryl
Glipzide	Glucotrol
Lidocaine	
Medications that may lead to Toursades de pointes	
Antiarrhythmic drugs:	
Hydroquinidine	Termium, Dihydroquinine
Class III Antiarrhythmics:	
Dofetilide	Tikosyn
Ibutilide	Corvert
Sotalol	Betapace, Sorine, Sotylize.
Amiodarone	Pacerone, Cordarone
Neuroleptics	
Phenothiazines	
Cyamemazine	Tercian
Levomepromazine	Nozinan, Levoprome, Detenler, Hirnamin, Levotomin, Neurocil
Benzamides	
Amisulpride	Solian
Sulpiride	Dogmatil
Tiapride	Tiapridal
Butyrophenones	
Droperidol	Inapsine, Droleptan, Dridol, Xomolix, Innovar
Haloperidol	Haldol
Other Neuroleptics	
Pimozide	Orap
Other Medications	
Diphémanil Metilsulfate	Prantal
Erythromycin IV	Erythrocin
Halofantrine	Halfan
Methadone	Dolophine, Methadose.
Mizolastine	Elina, Zehist
Moxifloxacin	Avelox
Pentamidine	Pentam, Nebupent.
Spiramycin	Rovamycine
Vincamine	Oxybral SR,
Lumefantrine	Coartem
Propafenone	Rythmol
Rizatriptan	Maxalt
Medications to consider	
Urological Agents: increase hypotensive effect. Increases the risk of orthostatic hypotension	
Afulzosin	Uroxtral
Doxazosin	Cardura, Doxadura, Cascor, Carduran
Prazosin	Minipress

Tamsulosin	Flomax
Terazosin	Hytrin
Amifostine	Ethyol

 • Imipramine (antidepressants, neuroleptics): antihypertensive effect and increased risk of orthostatic hypotension (additive effect) • Alpha blocker Antihypertensive Drugs: increases the hypotensive effect. Increased risk of orthostatic hypotension. • Dihydropyridines: hypotension • Dipyridamole IV (Persantine) • Phenobarbital (by extrapolation, primidone), Rifampicin (enzyme inducers): decrease in propranolol plasma concentrations with reduced clinical effects (increased hepatic metabolism). 	

Most frequently reported:
 
 • Asthenia • Cooling of extremities; Raynaud's Syndrome • Bradycardia • Sleep disorders (insomnia, nightmares) • Digestive disorders (gastralgia, nausea, vomiting, diarrhea) 	

Rarely reported:
 
 • Reduced atrioventricular conduction or increased intensity of an existing atrioventricular block • Heart failure • Worsening of an existing intermittent claudication • Thrombocytopenia • Severe drop in blood pressure • Bronchospasm • Hypoglycemia in at-risk patients (diabetes) • Central nervous system disorders: hallucinations, psychosis, mood changes, confusion, impotence • Paresthesias • Various skin manifestations, including psoriasiform rashes 	

On a biological level: In rare cases, the appearance of antinuclear antibodies (ANA) has been observed, exceptionally accompanied by symptoms of Lupus Syndrome, which resulted in the discontinuation of treatment.
	

7.10 Appendix I. Safety Measures Summary

Definitions

According to the ICH GCP E2 and E6 Guidelines, the definitions of adverse event and serious adverse event are:

Adverse event (AE)

Any untoward medical occurrence in a participant or clinical investigation participant administered a pharmaceutical product and which does not necessarily have a causal relationship with this treatment. An adverse event (AE) can therefore be any unfavourable and unintended sign (including an abnormal laboratory finding), symptom, or disease temporally associated with the use of an investigational product, whether or not related to the investigational product.

Serious adverse event (SAE)

Any untoward medical occurrence whether or not related to the investigational product that meets one of the six criteria:

- Results in death,
- Is life-threatening,
- Requires inpatient hospitalization or prolongation of existing hospitalization,
- Results in persistent or significant disability/incapacity,
- Is a congenital anomaly/birth defect,
- Is an important medical event requiring medical or surgical intervention to prevent serious outcome.

Suspected Unexpected Serious Adverse Reaction (SUSAR)

An event that is suspected as being related to the Investigational Product under investigation and is both serious and unexpected (the nature and severity of the event are not consistent with the information currently known about the medicinal product).

The National Cancer Institute Common Terminology Criteria (NCI CTC)

The National Cancer Institute Common Terminology Criteria for Adverse Events is a descriptive terminology which can be utilised for Adverse Event (AE) reporting.

AE and SAE Assessment

Causality

The causality of AEs (i.e., their relationship to intervention treatment) must be assessed by a suitable medically qualified Investigator at the Thompson Institute. Assessing causality requires considering whether there was a reasonable possibility that the event may have been caused by the intervention. In most cases, it is very difficult to categorically rule out a causal relationship. As such, the terms “related,” “possibly related” and “not related” will be interpreted as follows:

- “Related” – the reviewer is confident of the causal relationship (e.g. temporal association, existing safety knowledge of the product, clinical judgement);
- “Possibly related” – the reviewer is not confident of the causal relationship but tends to deem there is a positive causal relationship;
- “Not related” – the reviewer has no reason to believe there is a causal relationship at the time of the assessment (or tends to deem there is not a positive causal relationship).

Causality of an event may be re-evaluated by the reviewer at any time, e.g., when further evidence becomes available to confirm or refute an assessment of causality.

Severity

The Investigator will assess intensity for each AE and SAE reported during the study. The assessment will be based on the Investigator’s clinical judgement. The intensity of each AE and SAE recorded in the CRF should be assigned to one of the following categories:

- Mild: An event that is easily tolerated by the participant, causing minimal discomfort and not interfering with everyday activities or is considered mild by diagnosis.
- Moderate: An event that is sufficiently discomforting to interfere with normal everyday activities or is considered moderate by diagnosis.
- Severe: An event that prevents normal everyday activities or is considered severe by diagnosis.

An AE that is assessed as severe should not be confused with an SAE. Severity is a category utilised for rating the intensity of an event, and both AEs and SAEs can be assessed as severe. An event is defined as 'serious' when it meets one of the pre- defined outcomes as described in Section 10.1.

Recording of Adverse Events and Serious Adverse Events

Recording and reporting of an AE

All AEs will be documented on the case report form (CRF) or electronic CRF as per study requirements. The following types of information about the AE are commonly required:

1. Description of AE (a diagnosis is preferred);
2. Start date and end date;
3. Severity of the event;
4. Relationship to the investigational product;
5. Countermeasures;
6. Outcomes; and
7. Serious/non-serious.

The PI should try to establish a diagnosis of the event based on the signs and symptoms and/or other clinical information. If making a diagnosis is not possible, the PI will record the sign and/or symptom as an event.

1. The PI should follow the definition of the severity of adverse events as defined in the protocol.
2. The PI is required to assess the causal relationship between the IP and the AE.
3. The PI should ensure there is sufficient source data documentation to support the CRF entry.

Recording and reporting of a SAE

All the above procedures for recording and reporting of AEs also apply to that of SAEs. Any SAE that occurs during the study, whether related to trial treatment or not, must be reported by the PI within 24 hours after becoming aware of the event. The SAE is to be documented on the SAE reporting form contained in the individual case report form as stipulated in the protocol. The PI will document all available information regarding the SAE on the SAE reporting form. The initial SAE report should minimally include the following information or information otherwise specified in the protocol/study procedure manual:

1. Participant's study number;
2. Time and date of first starting the treatment;
3. Time and date of occurrence of the event;
4. A brief description of the event and countermeasures taken;
5. PI's opinion of the relationship with the IP.

The follow-up SAE report should be sent to the reporting bodies as soon as the follow-up information is available. The study site staff should follow the timeline for sending follow-up reports to sponsors, if any. The PI is responsible for complying with the requirements and reporting procedures of the HREC that granted approval of the study in relation to the reporting of SAEs. When preparing SAE reports to be submitted to the HREC, the study coordinator should ensure clear documentation of each specific report using the reporting procedure of the HREC that granted approval of the study. The PI is to manage any further action required by the HREC or regulatory body after reviewing the safety reports.

Handling in cases of Unresolved AEs and SAEs at completion or withdrawal

In the case of an AE or SAE, the participant will be appropriately referred and followed up with contact maintained until resolution or transfer of clinical care.

Procedures in case of medical emergency

All study staff members will receive medical emergency training, including CPR. The PI is responsible for ensuring all study staff members are aware of medical emergency procedures, and that there is relevant expertise available to manage medical emergencies at the study location. Medical emergencies will usually constitute an SAE and will be reported following the SAE reporting guidelines.

Within 24-48 hours of investigators receiving information that these events have occurred we will inform the HREC of the following:

- Any serious adverse events
- Any serious adverse drug reactions (ADRs)
- Any serious unexpected suspected adverse reactions (SUSARs)
- Any implemented amendments to protocol
- Any new safety information regarding oral ketamine use in published or unpublished studies relevant to the trial protocol.

We will submit **annual** reports to the HREC regarding:

- The progress of the study
- Any proposed amendments to protocol
- The secure maintenance of records and research data, and compliance with ethical conduct
- Upon **closure of the study**, we will inform the ethics committee and submit a closure report.

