The anti-anginal activity of propranolol hydrochloride likely stems from a reduction in left ventricular work and oxygen utilization due to the inhibition of cardiac sympathetic nerve stimulation. Propranolol hydrochloride has also demonstrated serotonin antagonism, though the therapeutic benefit of this property in centrally mediated disorders is still uncertain. As with other β -adrenoreceptor blocking agents, propranolol hydrochloride has negative inotropic effects, and therefore, it is contraindicated in patients with congestive heart failure.

Known adverse events

Propranolol hydrochloride is usually well tolerated, and side effects are transient in nature, rarely necessitating withdrawal of treatment. The most serious adverse reactions encountered are congestive heart failure and bronchospasm in susceptible patients. Common adverse reactions include fatigue and/or lassitude (often transient), bradycardia, cold extremities and exacerbation of Raynaud's phenomenon, sleep disturbances including vivid dreams/nightmares. Other less frequently reported adverse reactions include gastrointestinal disturbances (nausea, vomiting, diarrhoea, abdominal pain), congestive heart failure, dizziness, bronchospasm. Rare cases of thrombocytopenia and purpura have been reported. CNS symptoms including mood changes and hallucinations have been reported rarely. It should be noted that those symptoms have been reported among individuals taking propranolol every day for prolonged periods of time. Our study participants will be taking propranolol once a week, for 6 weeks.

Known contraindications or warnings:

- **Cardiovascular:**
 - o Congestive heart failure
 - o Right ventricular failure secondary to pulmonary hypertension
 - o Significant right ventricular hypertrophy
 - o Sick sinus syndrome
 - o Sinus bradycardia (less than 45 to 50 beats/minute)
 - o Second- and third-degree A-V block
 - o Hypotension
 - o Severe peripheral arterial circulatory disturbances
 - o Prinzmetal's angina
- **Hypoglycaemia, prolonged fasting and metabolic acidosis:**
 - o Propranolol must not be used in patients prone to hypoglycaemia, i.e. patients after prolonged fasting or patients with restricted counter regulatory reserves. In metabolic acidosis (e.g., in diabetes), the premonitory signs of hypoglycaemia may be masked in patients receiving hypoglycaemic agents.
- **Asthma/bronchospasm:**

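### Appendix I tests causality by 'reasonable possibility', but its categories code an event the reviewer merely leans against as 'Not related', so related events can be under-counted

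*Protocol*

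**What the plan says.** Protocol Appendix I (7.10), under Causality, sets the test: "Assessing causality requires considering whether there was a reasonable possibility that the event may have been caused by the intervention". It adds a caution: "In most cases, it is very difficult to categorically rule out a causal relationship". It then offers three terms as the consequence of those two sentences.

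- 'Related' needs confidence in the causal link.
- 'Possibly related' applies where "the reviewer is not confident of the causal relationship but tends to deem there is a positive causal relationship".
- 'Not related' has two limbs. The first is that "the reviewer has no reason to believe there is a causal relationship at the time of the assessment". The second, in brackets, is "or tends to deem there is not a positive causal relationship".

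The same appendix defines a SUSAR as "An event that is suspected as being related to the Investigational Product under investigation and is both serious and unexpected". It lists serious adverse drug reactions and SUSARs, beside serious adverse events, among the matters to be notified to the ethics committee. Each initial SAE report must carry the PI's opinion on the relationship to the product.

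**The concern.** The categories are meant to put the reasonable-possibility test into practice, and they do not. Under the test, a reviewer who thinks another cause more likely, but sees a genuine chance that the intervention contributed, should keep the event on the related side. Under the categories, that reviewer has only 'Not related' available.

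This is more than a wording matter because section 5.1 describes a single treatment arm. Without a comparator event rate, the investigator's judgement is the main way to separate harm caused by treatment from harm that would have occurred anyway.

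Alternative explanations are also close at hand. Section 4.1 describes nightmares, poor sleep and irritability as features of PTSD, while section 5.11 lists "sleep disturbances including vivid dreams/nightmares" among common reactions to propranolol. Participants keep their existing psychotropic medication. Section 5.11 also remarks that the listed symptoms were reported with prolonged daily use, whereas participants here take one dose a week. Each of these gives a reviewer grounds to lean against causation without being able to exclude it.

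The judgement is made when the event is recorded. An analysis plan cannot later recover a judgement that was made against the wrong threshold.

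**Working it through.** The protocol states no figure on causality, so there is nothing to reproduce numerically. The check sets the test beside the categories for each state of mind a reviewer could hold.

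| Reviewer's view | Meets the reasonable-possibility test? | Category under Appendix I |
|---|---|---|
| Confident the event was caused | Yes | Related |
| Not confident, leans towards causation | Yes | Possibly related |
| Sees a reasonable possibility, leans against causation | Yes | Not related (second limb) |
| No reason to believe in a link | No | Not related (first limb) |

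The test and the categories disagree only in the third row. The two limbs of 'Not related' also disagree with each other, since leaning against a link is not the same as having no reason to believe in one.

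**Direction.** Let A be the set of events that meet the stated test and B the set coded 'Related' or 'Possibly related'. Anyone who is confident of causation, or leans towards it, also holds that it is reasonably possible. Every event in B is therefore in A, and

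count(B) ≤ count(A), so shortfall = count(A) − count(B) ≥ 0.

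The shortfall is exactly the number of third-row events. It is zero if there are none, and it cannot be negative while the definitions are followed. In terms of the reviewer's probability of causation, this treats 'tends to deem' as roughly better than even. That is an interpretation, as the protocol states no probability. The ordering needs only that leaning towards a cause is a stronger belief than finding it reasonably possible.

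**Size.** An estimate would need the number of events, how reviewers' certainty is spread across them, and where a reasonable possibility begins. The protocol gives none of these. Any percentage would only restate its own assumptions, so none is offered.

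**What depends on the category, all from Appendix I:**

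- Recording of adverse events does not. Every event goes on the CRF.
- Reporting of SAEs does not. The PI reports within 24 hours whatever the causality, and the ethics committee hears of any SAE within 24–48 hours.
- The relationship entered on the CRF, the PI's opinion in the SAE report, and classification as a serious adverse drug reaction do.
- The suspected element of a SUSAR does too, if 'suspected' is read through the three categories. That is the natural reading, although the appendix does not say so.

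**The case against.** The strongest reply is that Appendix I asks the assessor only to consider whether a reasonable possibility existed. On that view it fixes no cut-off, and the three terms are simply how the consideration is applied. This does not remove the difficulty. The terms are introduced as following from the difficulty of ruling causation out, yet they allow the reviewer to discard a link that has not been ruled out.

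A second reply is that Appendix I only summarises an SOP (section 5.6), and the full SOP may define the categories better. That is possible, but the text shown gives complete definitions and would be followed as it stands. Causality may also be re-evaluated at any time. This helps only in part, because re-evaluation is optional and uses the same definitions.

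A third reply is that reviewers may not lean towards the illness at all. The definition of 'Related' points them to timing and to existing safety knowledge, which would draw listed reactions towards relatedness. This stands as a reason not to predict how often the problem will arise.

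A reader might infer more than the protocol supports in three ways:

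- *That harm goes unrecorded, or serious events escape the ethics committee.* They do not. Recording and SAE reporting do not depend on causality, and SAEs share the SUSAR notification window.
- *That nightmares, disturbed sleep or mood change would become missed SUSARs.* These are listed reactions (section 5.11, Appendix G). They are expected in nature and would not normally be SUSARs under any causality threshold, unless their severity went beyond what is known. They illustrate under-attribution of adverse events. The SUSAR consequence is confined to unlisted serious events.
- *That the threshold hides harm from trauma recall in particular.* Whether events are judged against the whole intervention or the product alone is a separate inconsistency in Appendix I. Changing the threshold would not settle it.

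**Conclusion.** The point holds as an inconsistency within Appendix I that biases attribution in one direction. Events with a reasonable but minority possibility of causation are coded 'Not related'. Counts of related adverse events, serious adverse drug reactions and SUSARs among unlisted serious events can therefore be too low and cannot be too high. The size is unknown and may be zero. The conclusion rests on reading 'tends to deem' as leaning one way or the other and, for SUSARs, on 'suspected' following the causality category. It is worth correcting because a single-arm trial relies heavily on attribution, but it does not compromise the capture of harm.

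**What to change.** In Appendix I, under Causality:

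1. Delete the bracketed second limb of 'Not related', and define that category as no reasonable possibility of a causal relationship.
2. Define 'Possibly related' as a reasonable possibility of causation, even if another cause is thought more likely.
3. State that both 'Related' and 'Possibly related' count as suspected for classifying adverse drug reactions and SUSARs, and for any summary of related events. The protocol specifies no such summary at present, so this only fixes the rule should one be produced.

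Carry the same wording into the CRF completion guidance and the underlying SOP. Do this before events are coded. Any already coded 'Not related' should be re-assessed under the revised definitions, which the existing re-evaluation provision allows.

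The cost is a few sentences. The downside is a somewhat higher reported rate of related events, some of which will in truth be due to the illness or to other medication. The protocol's own standard already accepts that.
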